a. Study design, including the sequence and timing of study procedures (distinguish research procedures from those that are part of routine care).

This is a prospective, randomized, non-blinded study. The outcome variable collection will be blinded. Subjects will be randomized (1:1:1:1) within 24 hours of admission for acute decompensated heart failure to one of four treatment groups:

Treatment Protocol:

1. Intermittent bolus (every 12 hrs) furosemide diuretic therapy
2. Continuous infusion furosemide diuretic therapy
3. Intermittent bolus (every 12 hrs) furosemide diuretic therapy plus infusion of low dose intravenous dopamine (3 µg/kg/min)
4. Continuous infusion furosemide diuretic therapy plus infusion of low dose intravenous dopamine (3 µg/kg/min)

Each treatment arm protocol is detailed as follows:

1. Intermittent bolus furosemide diuretic therapy:
 - a. If the patient is not on a prior diuretic dose, a standard dose of furosemide 40mg IV every 12 hrs, with total dose of 80 mg IV over 24 hrs will be initiated.
 - b. If the patient is already on a prescribed diuretic dose, their outpatient dose will be doubled and administered as the equivalent IV dose every 12 hrs. Note: standard furosemide dosing has a 2:1 oral to IV ratio when dosing.
 - i. Example: If the prescribed home dose is furosemide 80mg by mouth twice daily, the inpatient treatment dose will be the IV equivalent of furosemide 160 by mouth twice daily (double the home dose). Therefore, the inpatient treatment dose would be furosemide 80mg IV twice daily).
2. Continuous infusion furosemide diuretic therapy
 - a. If the patient is not on a prior diuretic dose, a standard dose of furosemide 80mg IV over 24 hrs, will be initiated.
 - b. If the patient is already on a prescribed diuretic dose, their outpatient dose will be doubled and administered as the equivalent IV dose, continuously over 24 hrs. Note: standard furosemide dosing has a 2:1 oral to IV ratio when dosing.
 - i. Example: If the prescribed home dose is furosemide 80mg by mouth twice daily (160mg total per day), the inpatient treatment dose will be the IV equivalent of furosemide 320mg total per day. Therefore, the inpatient treatment dose would be furosemide 160mg IV administered continuously over 24 hrs.

3. Intermittent bolus (every 12 hrs) furosemide diuretic therapy plus infusion of low dose intravenous dopamine (3 µg/kg/min)

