Participants will receive routine care for their acute decompensated heart failure. Currently, many practitioners utilize both intermittent and continuous furosemide infusions in this patient group. Low dose, or renal-dose dopamine is also a frequent adjunct to diuretics to aid in diuresis.

e. Justification for inclusion of a placebo or non-treatment group.

There is no placebo group.

f. Definition of treatment failure or participant removal criteria.

Subjects will be removed from the protocol for:

1. The development of hemodynamic instability including hypotension (SBP < 90), hypertensive emergency, or unstable arrhythmias (SVT or VT).
2. The development of pulmonary edema requiring inotropes or vasopressor or more than 50% inspired oxygen.
3. The development of acute coronary syndrome.
4. The development of acute kidney injury by KDIGO criteria as follows¹:
 - a. If the patient develops Stage II AKI (by KDIGO criteria), the study treatment will be held and a clinical decision will be made whether to resume or discontinue treatment drug
 - b. If the patient develops Stage III AKI (by KDIGO criteria), the study treatment will be discontinued and the patient will be classified as treatment failure and followed only for outcome recording.
5. The need for renal replacement therapy
6. New atrial fibrillation or other supraventricular tachyarrhythmia
7. Sustained ventricular arrhythmias

8. Requirement of furosemide dose increase beyond the study maximum of 200 IV twice daily (or 400 IV over 24 hrs), or the need for addition of thiazide diuretic.

g. Description of what happens to participants receiving therapy when study ends or if a participant's participation in the study ends prematurely.

Once the study period ends, or if the study ends prematurely, the patient will receive standard heart failure management at the discretion of the primary team. The patient will resume standard outpatient follow up as advised by the primary team at the time of discharge.

5. Inclusion/Exclusion Criteria

a. Inclusion Criteria :

1. Admission to the hospital for acute decompensated heart failure within 24 hours of enrollment into the study.
 - a. Diagnosis of heart failure as defined by the presence of at least 1 symptom (dyspnea, orthopnea, or edema) AND 1 sign (rales on auscultation, elevated jugular venous pulse, hepatojugular reflex, peripheral edema, ascites, pulmonary vascular congestion on chest radiography)
2. Patient ≥ 18 years of age

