Johns Hopkins as well as data from prior studies in patients admitted with ADHF, we estimate a sample size of approximately 63 patients per treatment arm. This translates to 63 patients assigned to the diuretic-only treatment arm (intermittent bolus and continuous) and 63 patients assigned to the low-dose dopamine arm (in addition intermittent bolus diuretic and continuous diuretic treatment). Taking into account drop-out rate, we plan to enroll 140 patients (70 per treatment arm; 34 per specific treatment strategy).

4. Randomization:

- a. Patients will be randomized in a blinded fashion to one of four treatment arms upon enrollment. We plan to perform block randomization into the treatment arms and plan to stratify patients by race, CKD status, and receipt of IV contrast dye (during the same admission), as these factors are felt to be significantly associated with the development of AKI.

5. Analysis of Secondary Endpoints:

- a. Summaries of continuous variables will be displayed using the mean, standard deviation, and median. For nominal variables, the number and frequency of subjects in each category will be presented. Statistical tests with p-values < 0.05 will be considered statistically significant, unless otherwise stated.

b. Early stopping rules.

A study subject will be removed from the trial if the above mentioned scenarios from Section 5 were to occur:

- i. The development of hemodynamic instability including hypotension (SBP < 90), hypertensive emergency, or unstable arrhythmias (SVT or VT)
- ii. The development of pulmonary edema requiring inotropes or vasopressor or more than 50% inspired oxygen.
- iii. The development of acute coronary syndrome.
- iv. The development of acute kidney injury as follows:
 - a. If the patient develops Stage II AKI (by KDIGO criteria)¹, the study treatment will be held and a clinical decision will be made whether to resume or discontinue treatment drug
 - b. If the patient develops Stage III AKI (by KDIGO criteria)¹, the study treatment will be discontinued and the patient will be classified as treatment failure and followed only for outcome recording.
 - i. The need for renal replacement therapy
 - ii. New atrial fibrillation or other supraventricular tachyarrhythmia
 - iii. Sustained ventricular arrhythmias

- v. Requirement of furosemide dose increase beyond the study maximum of 200 IV twice daily (or 400 IV over 24 hrs), or the need for addition of thiazide diuretic.

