All patients will be admitted to telemetry floor beds for close monitoring of hemodynamic state. All patients will undergo vital sign checks every 4-8 hrs depending on clinical stability. Standard of care for inpatient acute heart failure management includes twice daily basic metabolic profile check to assess renal function and electrolytes. A standardized electrolyte replacement protocol will be enforced for all patients to minimize the risk of cardiac arrhythmias in the setting of diuresis. In patients whose GFR is below and/or creatinine is above the cutoff for the standard electrolyte repletion protocol, this will be managed by the primary team physicians. In addition, the

above stated exclusion criteria are designed to minimize enrollment of patients who are apt to have side effects.

A subject will not be considered for enrollment if they have any signs of hemodynamic instability (please refer to Exclusion criteria). This includes hypotension for any reason (SBP < 90), hypertensive emergency (SBP >200 or signs of end-organ damage), supraventricular tachycardias (atrial fibrillation, atrial flutter) that are not responsive to rate control therapies, or ventricular arrhythmias beyond occasional PVCs or NSVT.

In the dopamine strategy group, if the subject develops tachycardia as defined by heart rate of >120 beats per min the infusion will be stopped. After 3 hours, if heart rate is < 120 beats per min, the IV infusion will be restarted at 1 µg/kg/min (<50% of the previous dose). If the heart rate is >120 beats per min after 3 hours or if tachycardia recurs, then the infusion will be terminated and this will be captured as “treatment failure.”

c. Plan for reporting unanticipated problems or study deviations.

All unanticipated problems such as transfers to the CCU, atrial or ventricular arrhythmias, acute coronary syndrome, or acute renal failure requiring renal replacement therapy will be reported within 48 hrs and reviewed by the study team. All deaths will be reviewed by the study team and reported to the IRB.

d. Legal risks such as the risks that would be associated with breach of confidentiality.

e. Financial risks to the participants.

There is no financial risk to the patients in this study.

9. Benefits

a. Description of the probable benefits for the participant and for society.

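### For new AF or SVT above 120/min in a dopamine arm, Section 8.b can require a restart where Sections 4.f and 7.b require removal, and no precedence is stated

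*Combined protocol and SAP*

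**What the plan says.** Section 8.b (Steps taken to minimize the risks) gives a rule for the dopamine arms only, in three parts:

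- Trigger: "In the dopamine strategy group, if the subject develops tachycardia as defined by heart rate of >120 beats per min the infusion will be stopped".
- Restart: "After 3 hours, if heart rate is < 120 beats per min, the IV infusion will be restarted", at a stated lower dose.
- Permanent stop: "If the heart rate is >120 beats per min after 3 hours or if tachycardia recurs, then the infusion will be terminated", and the event is recorded as treatment failure.

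Section 4.f is headed as the definition of treatment failure or of removal. It opens with "Subjects will be removed from the protocol for" and lists as item 6 "New atrial fibrillation or other supraventricular tachyarrhythmia". It applies to all four arms.

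The Early stopping rules in Section 7 (lettered b, cited here as 7.b) repeat that event under the lead-in "A study subject will be removed from the trial if the above mentioned scenarios from Section 5 were to occur". Section 5 holds the eligibility criteria; the list referred to is in 4.f.

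Treatment failure is used in two other places. Section 4.a (Maximum Diuretic Dose) applies it to patients who need more diuretic than the protocol permits and takes them out of the study. Section 4.f item 4b applies it to Stage III AKI, stops study treatment, and keeps the patient for outcome recording only.

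**The concern.** The trigger in 8.b is a heart rate; the trigger in 4.f item 6 is a rhythm. New fast AF or SVT satisfies both. One rule then leads, on a condition, to renewed exposure to the study drug, and the other takes the subject off the protocol.

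Section 8.a lists fast or irregular heart rate among the common risks of low-dose dopamine, so the overlap is foreseeable. Whoever manages the patient cannot obey both instructions, and the one followed decides whether a patient is re-exposed to dopamine after a named adverse event.

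There is also a data question. The pause-and-restart rule exists only in the dopamine arms of an open-label trial. Dopamine exposure and the recorded reason for stopping could therefore depend, on that side of the comparison alone, on which section was consulted. The primary analysis is intention-to-treat on creatinine at 72 hours, so it matters whether a patient who leaves under one of these rules still contributes a 72-hour value.

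**Working it through.** No statistical figure is at issue, so the check sets the passages side by side.

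**Step 1. Scope and trigger.**

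| | 8.b | 4.f item 6 (repeated in 7.b) |
|---|---|---|
| Applies to | dopamine arms | all arms |
| Trigger | heart rate >120, any rhythm | new AF or other SVT, any rate |
| Acts on | the dopamine infusion | the subject |
| Restart | yes, if rate <120 after 3 hours | none |
| Wording | mandatory | mandatory |

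Item 6 cannot be narrowed to unstable rhythms, because item 1 of the same list already covers unstable SVT and VT.

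**Step 2. Branches for a dopamine-arm patient with new AF or SVT above 120.**

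- *Rate below 120 after 3 hours.* 8.b restarts dopamine; 4.f and 7.b have removed the subject. The results are opposite. For example, new AF at 130/min that is still AF at 110/min three hours later meets both rules.
- *Rate still above 120, or tachycardia recurs.* Both rules end dopamine. Only the classification differs: treatment failure under 8.b, removal under 4.f and 7.b.

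Two cases do not conflict. A rate above 120 without AF or SVT does not meet item 6, and new AF or SVT at or below 120 does not meet 8.b.

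**Step 3. Is precedence stated?** No section cross-refers the two rules. Neighbouring text does not settle it:

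- The paragraph before the 8.b rule counts AF and flutter among supraventricular tachycardias, so tachycardia in 8.b is not evidently sinus only.
- Item 4a of 4.f lets treatment be held and possibly resumed for Stage II AKI, so appearing on that list does not always mean permanent removal.
- 7.b prints the AF item beneath the AKI item. That may come from the text extraction, and 4.f is sufficient without it.

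**Step 4. Treatment failure.**

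| Place | Event | Consequence |
|---|---|---|
| 4.a | diuretic need beyond the maximum, or an added agent | out of the study |
| 4.f item 4b | Stage III AKI | treatment stopped, outcomes still recorded |
| 8.b | persistent or recurrent tachycardia | infusion terminated; furosemide not mentioned |

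The 8.b event is missing from the 4.f list, although that list is headed as the definition. Only item 4b expressly keeps recording outcomes. A sentence closing 7.b says the investigators will follow these patients for the duration of the study. It may be meant for removed subjects, but it does not mention the 72-hour measurements, and it follows a list of reasons for removal from the trial.

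**Step 5. Size.** The plan is for 70 dopamine patients of 140. The documents give no rate of new AF or SVT. As an assumption only, if 3% to 10% had new AF or SVT above 120:

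- 0.03 × 70 = 2.1
- 0.10 × 70 = 7

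So about 2 to 7 patients would enter Step 2. This is a ceiling for the restart conflict at those assumed rates, because it includes patients whose rate stays high.

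The restart dose itself is internally consistent: 1/3 = 33% of the assigned 3 µg/kg/min, which agrees with the stated limit of under 50%.

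**The case against.** The strongest reply is that the rules can be read together. 4.f acts on the subject and 8.b on one infusion. A subject removed for new AF is already off protocol when the 3-hour check falls due, so no protocol infusion remains to restart. The same overlap arises for a rate above 120 with systolic pressure below 90 or an acute coronary syndrome, and few would read 8.b as overriding removal there. The paragraph before the 8.b rule also names AF and flutter when it means them.

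This reading is plausible, but the protocol does not state it. The appeal to the more specific rule also cuts both ways: 4.f is specific to rhythm, 8.b to the dopamine arms. Review by the study team of atrial arrhythmias, reportable within 48 hours under 8.c, limits inconsistent handling but comes after the 3-hour decision may have been taken.

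Other parts of the reply stand, and they rule out stronger readings that a reader might infer:

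- *Every rate above 120 leads to a restart.* It does not; restart requires a rate below 120 after 3 hours.
- *Every dopamine patient with fast AF or SVT gets opposite dopamine instructions.* Only the branch with a falling rate does.
- *Furosemide continues under one rule and stops under the other.* Continuation under 8.b is inferred from silence. Under 4.g, early exit leads to standard care at the primary team's discretion, which may include furosemide.
- *Centres will differ.* The document is one institution's IRB form and names no other site.

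**Conclusion.** Wrong as written: an internal contradiction in a participant-safety rule. It applies to a dopamine-arm patient with new AF or SVT above 120/min whose rate is below 120 after 3 hours. In the other branch, dopamine ends either way and only the classification is inconsistent. Separately, treatment failure has no single definition or consequence, and this also touches dopamine patients whose tachycardia is not AF or SVT.

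The number affected is unknown and probably small: some part of those among the planned 70 dopamine patients who develop new AF or SVT. The conclusion rests on the wording alone and needs no event rate.

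A reader might go on to infer bias in the primary creatinine comparison. The documents do not support that. Crossover is permitted, the analysis is by intention to treat, and nothing shows that a few altered exposures would move the result. The open matter for the analysis is narrower: whether 72-hour outcomes are obtained for patients stopped or removed under these rules.

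**What to change.** Reconcile 8.b with 4.f and 7.b by amendment:

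1. State which rule governs when a dopamine-arm patient meets both, and cross-refer the sections.
2. State for each trigger whether dopamine alone or all study treatment stops.
3. Give treatment failure one definition and one consequence, used alike in 4.a, 4.f, 7.b and 8.b.
4. State whether patients stopped or removed for any of these reasons still have 72-hour outcomes recorded for the intention-to-treat analysis.
5. Correct the reference in 7.b to Section 5, and check where the AF item sits in that list.

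Which rule should govern new AF or SVT, and on what conditions, is for the sponsor's clinicians; no view is taken here. The cost is a few sentences in an amendment. Items 1 to 3 and 5 need no new procedure. Item 4 adds none if the existing 72-hour assessment is kept for these patients.
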